9 APPENDICES

9.1 Appendix 1: Handling of the Human Leukocyte Antigen (HLA) Mismatching

For the comparison of the HLA types between the donor and the recipient, the following steps should be done to calculate the number of HLA mismatches:

1. If the entry for a locus is a numeric code and a dash (or missing), then the dash for that locus is to be replaced (for calculation only) by the numeric code (homozygote).
2. The following rules should be applied when calculating the number of mismatches within a HLA A, B, and DR locus:
 - If both codes are missing in either the donor or recipient, the number of mismatches is unknown (missing)
 - If the two codes are non-missing and identical for the recipient and the donor (without regard to the order) or the donor is homozygote and the donor code matches either one of the recipient's codes then the number of mismatches is 0.

Examples:

Donor	Recipient	Mismatch
A1 A2	A2 A1	0
A2 A2	A2 A1	0

- If one code from the donor exists in the recipient but the other code is different between the donor and recipient or the donor has identical codes (homozygote) but they don't match either code in the recipient, then the number of mismatches is 1.

Examples:

Donor	Recipient	Mismatch
A2 A3	A2 A1	1
A2 A3	A2 A2	1
A2 A2	A3 A4	1
A2 A2	A1 A1	1

- If the donor is not homozygote and all codes are different between the donor and the recipient then the number of mismatches is 2.

Example:

Donor	Recipient	Mismatch
A1 A2	A3 A4	2

3. If the number of mismatches from any of the three loci are missing, then total number of HLA mismatches is missing. Otherwise the total number of HLA mismatches is the sum of the mismatches from the three loci.

An example following rules 1-4 above is provided below:

Donor: (broad types)	HLA A		HLA B		HLA DR	
	A11	A10	B5	B5	DR5	DR6
Recipient: (broad types)	HLA A		HLA B		HLA DR	
	A10	A19	B12	B5	DR5	DR7
Mismatch:	HLA A	HLA B	HLA DR	Total		
	1	0	1	2		

9.2 Appendix 2: Futility Analysis

The decision rule for stopping the trial based on efficacy is outlined below:

1. At the interim look, suppose we have cumulative n_i ($i = 0, 1$) subjects from treatment i ($i = 0$ for placebo and $i = 1$ for vaccine). The cumulative number of subjects with viremia in treatment i will be denoted as s_i ($i = 0, 1$).
2. The additional number of subjects with viremia at the end of trial could be any integer between 0 and $N - n_i$ for treatment i , where N is the total number of subjects planned for each group. The probability that there are additional k_0 subjects with viremia in the placebo group and k_1 subjects with viremia in the vaccine group at the end of trial is

$$p(k_0, k_1) = \binom{N - n_0}{k_0} \frac{B(\alpha + s_0 + k_0, \beta + N - s_0 - k_0)}{B(\alpha + s_0, \beta + n_0 - s_0)} \\ \times \binom{N - n_1}{k_1} \frac{B(\alpha + s_1 + k_1, \beta + N - s_1 - k_1)}{B(\alpha + s_1, \beta + n_1 - s_1)} \quad (\text{A})$$

where α and β are some arbitrary prior parameters and $B(a, b) = \int_0^1 x^{a-1}(1-x)^{b-1}dx$ is a beta function. (For this study, we use $\alpha = 0.6$, $\beta = 0.4$.) The reduction in relative risk is estimated as $rrr = 1 - \frac{s_1 + k_1}{s_0 + k_0}$ with probability (A) above.

3. Sum up the probabilities with which $rrr \geq 25\%$ over all possible values of k_0 and k_1 to get the predictive probability PP :

$$BPP = \sum_{k_0=0}^{N-n_0} \sum_{k_1=0}^{N-n_1} p(k_0, k_1) \text{step}(rrr \geq 25\%)$$

where the *step function* = 1 if $rrr \geq 25\%$ and 0 otherwise.

If $BPP \leq \text{cutoff}$ then ending the study is indicated. Otherwise the study should be continued. Here the *cutoff* = 20% is an empirical value determined by simulation studies.

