7.4 Analysis of Efficacy

7.4.1 Analysis of Primary Endpoint

7.4.1.1 Primary Analysis of Primary Efficacy Endpoint

The primary efficacy endpoint is the proportion of subjects with CMV viremia which is defined as plasma viral load ≥ 1000 IU/mL assessed by central assay through one year post first Study Drug injection. CMV viral load tests are scheduled once every 2 weeks for the first 8 tests starting 100 days from transplant and subsequently once per month for 7 more tests. In addition, a subject may have unscheduled tests (suspect CMV syndrome or CMV tissue-invasive disease) by the local laboratory so that the subject can be treated promptly with antiviral therapy (AVT) if needed. Everytime a local laboratory is performed, the sample should also be sent to the central laboratory for assessment. The CMV viral load collected from the central laboratory after first injection (Day 1) through day 380 ($=365+14+1$) that were collected as scheduled or unscheduled assessments will be utilized.

A patient who discontinue the study without a positive CMV viral load will be imputed as having a CMV viremia. A patient who has more than one time with viral load ≥ 1000 IU/mL by central assay will be counted once in this summary. Any unscheduled central laboratory values within the window will be included.

A Cochran-Mantel-Haenszel (CMH) test at the 1-sided 5% level stratified by use of anti-thymocyte globulin (ATG) and by receipt of a kidney from a living or deceased donor will be used to analyze the primary endpoint of CMV incidence rate.

The null and alternative hypotheses for this comparison are:

H0: Common Odds Ratio = 1.

H1: Common Odds Ratio < 1.

The odds ratio is defined as the ratio of odds of viremia in the ASP0113 group to that in the placebo group. The 1-sided p-value with the 2-sided exact 90% confidence interval for the

common odds ratio will be calculated (in SAS specifying the comor option in the exact statement of proc freq).

The primary analysis will be conducted for the FAS population.

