7.8 Interim Analysis (and Early Discontinuation of the Clinical Study)

No interim analysis evaluating the efficacy results are planned. The safety data will be monitored by the DMC according to the DMC Charter. Futility analyses with first 50 subjects and with 90 subjects were conducted ([Appendix 2](#)). The details will be described in the clinical study report.

At each futility analysis, Bayesian predictive probability of success (*BPP*) that the overall results of the trial will achieve the desired outcome, i.e., viremia rate on ASP0113 is at least 25% less than that on placebo, will be calculated based on the accrued data. If $BPP \leq 0.20$, then we conclude ASP0113 meets futility criterion.

The 20% cut-off for BPP is determined by simulation studies. The simulation studies cover the following scenarios: for each placebo viremia rate of 0.40, 0.46, and 0.51 the reduction in viremia due to ASP0113 run from 0% (no effect), 10% (marginal reduction), 25% (meaningful reduction), and 45% (significant reduction). Under each scenario, BPP is calculated at each interim look. The 20% cutoff produces satisfactory overall operating

characteristics of stopping the study early when there is little effect and preserving the power when ASP0113 shows the hypothesized effect.

A Data Monitoring Committee (DMC), external from the Sponsor, will be established to review safety and efficacy data at each interim look. A detailed description of the DMC, its role in this clinical trial, and the timing of the scheduled reviews will be provided in the DMC Charter.

Production of tables and listings will be performed by the independent statistician at Astellas / independent Data Analysis programmer at [REDACTED]. No member of the clinical trial team will have access to the reporting data base or will review the final tables and listings created for the DMC.

The primary responsibility of the DMC will be to monitor the trial for safety and futility concerns. The DMC will not stop the trial based on efficacy advantages. Therefore, the significance level need not be adjusted for the interim looks.

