9.3 Appendix 3: Simulation Studies

The number of incidence x has the binomial distribution given the probability parameter π :

$$p(x|\pi) = \binom{n}{x} \pi^x (1 - \pi)^{n-x}, \quad x=0, 1, \dots, n \quad (1)$$

We assume the distribution for π follows beta distribution with parameters α and β :

$$p(\pi) = \text{Beta}(\alpha, \beta) = \frac{1}{B(\alpha, \beta)} \pi^{\alpha-1} (1 - \pi)^{\beta-1}, \quad 0 < \pi < 1 \quad (2)$$

where $B(\alpha, \beta)$ is a beta function

$$B(\alpha, \beta) = \frac{\Gamma(\alpha)\Gamma(\beta)}{\Gamma(\alpha+\beta)}.$$

Then the posterior distribution is a beta distribution as well

$$p(\pi|x) = \frac{p(x|\pi)p(\pi)}{p(x)} \sim \pi^x (1 - \pi)^{n-x} \pi^{\alpha-1} (1 - \pi)^{\beta-1} \\ \sim \pi^{(\alpha+x)-1} (1 - \pi)^{(\beta+n-x)-1} = \text{Beta}(\hat{\alpha}, \hat{\beta}), \quad (3)$$

where $\hat{\alpha} = \alpha + x$ and $\hat{\beta} = \beta + n - x$. This conjugate feature of Beta distribution will be used in the simulations below.

We start with a hypothetical scenario where the viremia incidence rate π_i is known ($i = 0$ for placebo and $i = 1$ for vaccine). Let n_1 and n_2 be the cumulative number of subjects each group has at the first and second interim look, respectively. And let N denote the number of subjects each group has at the end of trial.

1. The data at the first interim look will be simulated by drawing $n_1 = 25$ random samples from $\text{binomial}(n_1, \pi_i)$ ($i = 0, 1$). The number of incidence will be denoted as s_{1i} ($i = 0, 1$).
2. Based on the conjugate feature of the beta prior, the distribution of the viremia incidence rate should be updated to $\text{Beta}(\alpha + s_{1i}, \beta + n_1 - s_{1i})$ ($i = 0, 1$) at the first interim look. Draw J random samples for θ_{1i} from the above beta distribution, where θ_{1i} is a random sample of the viremia incidence rate for the i th group ($i = 0, 1$) at the first interim look.
3. For each θ_{1i} draw M random samples from $\text{binomial}(N - n_1, \theta_{1i})$ to simulate the outcomes at the end of trial when all subjects are recruited and followed up for the endpoint ($i = 0, 1$). The number of additional (plus) incidence will be denoted as ps_{1i} ($i = 0, 1$). Consequently, the reduction in relative risk is estimated as $rrr = 1 - \frac{s_{11} + ps_{11}}{s_{10} + ps_{10}}$.

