4. Compute the proportion P of $rrr \geq 25\%$ over the $J \times M$ random samples. If $P \leq \text{cutoff}$, here the cutoff a threshold value (say 20%) to be determined the simulation studies, then stop the study. Otherwise proceed to the step below.

5. Draw additional $n_2 - n_1 = 20$ random samples from $binomial(n_2 - n_1, \pi_i)$ ($i = 0, 1$). Suppose the number of incidence is s_{2i} ($i = 0, 1$). The distribution of the viremia incidence rate is now updated to $Beta(\alpha + s_{1i} + s_{2i}, \beta + n_2 - s_{1i} - s_{2i})$ ($i = 0, 1$) at the second interim look. Draw J random samples for θ_{2i} from the above beta distribution, where θ_{2i} is a random sample of the viremia incidence rate for the i th group ($i = 0, 1$) at the second interim look.
6. For each θ_{2i} draw M random samples from $binomial(N - n_2, \theta_{2i})$ to simulate the outcomes at the end of trial when all subjects are recruited and followed up for the endpoint ($i = 0, 1$). The additional number of incidence will be denoted as ps_{2i} ($i = 0, 1$). The reduction in relative risk is estimated as $rrr = 1 - \frac{s_{11} + s_{21} + ps_{21}}{s_{10} + s_{20} + ps_{20}}$.
7. Compute the proportion P of $rrr \geq 25\%$ over the $J \times M$ random samples. If $P \leq cutoff$ then stop the study. Otherwise continue the study to the end when all N subjects are enrolled and followed up for the end point one year after the first injection of study drug.
8. Repeat steps 1-7 R times to estimate the probability of stopping the study at first and second looks for a given hypothetical scenario as the proportion of stopping over the R repetitions.

We repeat the process for various scenarios. Specifically, the scenarios considered are (1) no effect (incidence rates in the two groups are equal), (2) minor effect (10% reduction in incidence rate), (3) meaningful effect (25% reduction in incidence rate), and (4) significant effect (45% reduction in incidence rate). The incidence rates for placebo group considered are 46% and 51%. For each scenario, we run the simulations with $R=1000$, $J=1000$, and $M=1000$.

Simulation results are presented in the tables below.

Table 1: The cumulative probability of the Bayesian predictive probability (BPP) that the viremia incidence rate is at least 25% lower in ASP0113 than that in placebo is less than 25% (futility) at each interim look for different scenarios.

Viremia incidence rate		Cumulative probability of futility			Prob of success

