Placebo	ASP0113	1 st look	2 nd look	End of study	End of study
0.51	0.51	0.680	0.921	0.976	0.024
	0.46	0.528	0.827	0.908	0.092
	0.38	0.285	0.520	0.636	0.364
	0.28	0.083	0.155	0.175	0.825
0.46	0.46	0.656	0.882	0.961	0.039
	0.41	0.511	0.766	0.868	0.132
	0.34	0.275	0.510	0.609	0.391
	0.25	0.079	0.172	0.185	0.815

Table 2: The cumulative probability of the Bayesian predictive probability (BPP) that the viremia incidence rate is at least 25% lower in ASP0113 than that in placebo is less than 20% (futility) at each interim look for different scenarios.

Viremia incidence rate		Cumulative probability of futility			Prob of success
Placebo	ASP0113	1 st look	2 nd look	End of study	End of study
0.51	0.51	0.632	0.905	0.971	0.029
	0.46	0.474	0.800	0.897	0.103
	0.38	0.247	0.479	0.614	0.386
	0.28	0.064	0.138	0.159	0.841
0.46	0.46	0.608	0.865	0.957	0.043
	0.41	0.454	0.747	0.862	0.138
	0.34	0.246	0.470	0.594	0.406
	0.25	0.059	0.149	0.164	0.836

Table 3: The cumulative probability of the Bayesian predictive probability (BPP) that the viremia incidence rate is at least 25% lower in ASP0113 than that in placebo is less than 15% (futility) at each interim look for different scenarios.

Viremia incidence rate		Cumulative probability of futility			Prob of success
Placebo	ASP0113	1 st look	2 nd look	End of study	End of study
0.51	0.51	0.579	0.879	0.966	0.034
	0.46	0.425	0.760	0.885	0.115
	0.38	0.195	0.435	0.590	0.410
	0.28	0.046	0.116	0.141	0.859
0.46	0.46	0.554	0.846	0.954	0.046
	0.41	0.385	0.710	0.850	0.150
	0.34	0.205	0.421	0.567	0.453
	0.25	0.045	0.118	0.137	0.863

When there is no treatment effect (0.46 vs 0.46 or 0.51 vs. 0.51) the $BPP \leq 0.25$ criterion results in >65% chance to terminate the study; $BPP \leq 0.2$ criterion results in about 61% chance while $BPP \leq 0.1$ offers less than 50% chance which is too low to serve our purpose since the goal of the interim analysis is to stop early when there is no treatment effect.

When there is a fair treatment effect (25% reduction in viremia rate) (0.46 vs 0.34 or 0.51 vs. 0.38) the $BPP \leq 0.25$ criterion results in 30% chance to terminate the study while $BPP \leq 0.2$ criterion results in about 23% chance.

The chance of mistakenly terminating study at interim for the 0.46/0.25 and 0.51/0.28 scenarios is about 7% to 9% for the 0.2 criterion and >10% for the 0.25 criterion.

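### The second-look and end-of-study figures in SAP Appendix 3 do not follow from its own futility algorithm; incomplete follow-up at the looks is a smaller, separate limitation

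*SAP*

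**What the plan says.** Protocol 7.8 and SAP 3.2 set two looks, when 50 and then 90 subjects have completed the month 6 visit. Under Protocol 7.8.2 each look uses whatever data those subjects have, and futility is met if the Bayesian predictive probability (BPP) is 0.20 or less. SAP 7.8 describes the BPP as the probability that "the overall results of the trial will achieve the desired outcome", meaning viremia at least 25% lower on vaccine, and says the cutoff was set by simulation. It also records that "Futility analyses with first 50 subjects and with 90 subjects were conducted" and leaves the details to the CSR.

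On events still to come, Appendix 2 says: "The additional number of subjects with viremia at the end of trial could be any integer between 0 and" N − n_i. Appendix 3 then gives the simulation. "The data at the first interim look will be simulated by drawing" 25 subjects per arm at the scenario rate. Step 5 adds 20 per arm at the same rate. Step 7 carries surviving trials on until all N subjects are "followed up for the end point one year after the first injection of study drug".

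Table 2 prints the cumulative probability that the BPP "is less than 20% (futility) at each interim look for different scenarios". The text after Table 3 says: "The chance of mistakenly terminating study at interim for the 0.46/0.25 and 0.51/0.28 scenarios is about 7% to 9% for the 0.2 criterion". For the primary endpoint, SAP 7.4.1.1 uses "The CMV viral load collected from the central laboratory after first injection (Day 1) through day 380".

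**The concern.** Tables 1 to 3 are the documented justification for the 0.20 cutoff. For the 0.46 vs 0.25 and 0.51 vs 0.28 scenarios, Table 2 shows wrongful stopping of 0.059 and 0.064 at look 1 and 0.149 and 0.138 by look 2. The prose says 7% to 9%, which is neither. A reader cannot tell which figure describes the rule, and the CSR may repeat the wrong one.

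There is also a question of what the rule is applied to. A subject enters a look at about analysis Day 151 (Visit 10, SAP 7.9.3), with 6 or 7 of 15 scheduled viral loads done, while the endpoint window closes at Day 380. Neither appendix has a term for the part of the window not yet observed.

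**Working it through.** **Inputs.** Prior α = 0.6, β = 0.4 (Appendix 2); 25 then 45 per arm, R = 1000 (Appendix 3); cutoff 0.20 (SAP 7.8); N = 70 per arm (SAP 4, since Appendix 3 gives no value for N). End-of-study success is read as an unstopped trial with an observed relative reduction of at least 25%.

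**Rule.** For arm i with s_i events among n_i subjects,

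P(k_i) = C(N − n_i, k_i) · B(α + s_i + k_i, β + N − s_i − k_i) / B(α + s_i, β + n_i − s_i).

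BPP is the sum of P(k_0)·P(k_1) over all pairs with 1 − (s_1 + k_1)/(s_0 + k_0) ≥ 0.25. Stop if BPP ≤ 0.20. Stopping probabilities were enumerated exactly, carrying the unstopped outcomes of look 1 into look 2 with the extra 20 per arm.

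**Table 2, cumulative stopping, printed / enumerated.**

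| Placebo vs vaccine | Look 1 | Look 2 | Look 2 gap |
|---|---|---|---|
| 0.51 vs 0.51 | 0.632 / 0.634 | 0.905 / 0.838 | 0.067 |
| 0.51 vs 0.46 | 0.474 / 0.477 | 0.800 / 0.681 | 0.119 |
| 0.51 vs 0.38 | 0.247 / 0.241 | 0.479 / 0.363 | 0.116 |
| 0.51 vs 0.28 | 0.064 / 0.061 | 0.138 / 0.083 | 0.055 |
| 0.46 vs 0.46 | 0.608 / 0.598 | 0.865 / 0.805 | 0.060 |
| 0.46 vs 0.41 | 0.454 / 0.441 | 0.747 / 0.635 | 0.112 |
| 0.46 vs 0.34 | 0.246 / 0.238 | 0.470 / 0.353 | 0.117 |
| 0.46 vs 0.25 | 0.059 / 0.068 | 0.149 / 0.092 | 0.057 |

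The first look reproduces, so the rule has been read correctly. The second-look gaps are not simulation noise. For 0.46 vs 0.25 the standard error is √(0.092 × 0.908 / 1000) = 0.0091, and 0.057 / 0.0091 = 6.2. For 0.46 vs 0.46 the ratio is 4.8.

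**Could another reading give the printed column?** N = 64 gives 0.097, 0.088 and 0.818 where 0.149, 0.138 and 0.865 are printed. Other priors and other second-look sizes also fail. Basing look 2 on only the 20 new subjects per arm gives 0.147 and 0.140 for the two strong-effect rows, but misses the other six (0.727 where 0.800 is printed). No cause was found.

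**Other tables.** For 0.46 vs 0.25 by look 2, Table 1 (cutoff 0.25) prints 0.172 against 0.115, and Table 3 (cutoff 0.15) prints 0.118 against 0.068. Table 2 success is 0.386 against 0.460 (0.51 vs 0.38), 0.406 against 0.473 (0.46 vs 0.34) and 0.836 against 0.868 (0.46 vs 0.25). In Table 3 the 0.46 vs 0.34 row gives 0.567 + 0.453 = 1.020 for two outcomes that should sum to 1.

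**Prose.** The enumerated cumulative values by look 2 are 0.083 and 0.092 at cutoff 0.20, consistent with 7% to 9%. At cutoff 0.25 they are 0.106 and 0.115, consistent with the stated figure above 10%. The no-effect figure of about 61% is a first-look value (printed 0.608 and 0.632). The prose therefore mixes looks without saying so.

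**Incomplete follow-up.** The documents give neither accrual nor f, the share of one-year events seen by month 6. The Synopsis dates (first subject in 4Q2013, last out of the primary period 2Q2017) span about 40 to 45 months; less 13 months to Day 395, that leaves 27 to 32 months of accrual. The simulation assumes uniform accrual, f from 0.7 to 0.3, equal timing in both arms and all available data used. By look 2:

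- wrongful stopping (0.46 vs 0.25) goes from 9.2% to about 10–12%;
- no-effect stopping (0.46 vs 0.46) goes from 80.5% to about 76–80%;
- success (0.46 vs 0.25) goes from 0.868 to about 0.84–0.86.

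If nothing after month 6 were available, wrongful stopping would be 13.0% at f = 0.7 and 17.2% at f = 0.5. With unequal timing at 30 months (placebo f = 0.7), a vaccine early share 20% lower gives about 8% wrongful and 75% no-effect stopping; 20% higher gives about 12% and 83%.

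**The case against.** The best defence is that little turns on this. Both looks are done, they could stop only for futility, and SAP 7.8 already promises the details in the CSR. The prose figures quoted for wrongful stopping at the two cutoffs hold under complete follow-up. For the design effect the printed table is pessimistic: it shows more wrongful stopping (0.149) and less success (0.836) than the algorithm gives. The rule compares relative rates, so an equal lag in both arms largely cancels, and the remaining shift of a few points rests entirely on assumed timing.

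All of that stands as a limit on the consequences. It does not make the tables right, and the error is not pessimistic everywhere: 0.865 against 0.805 overstates the rule's ability to stop a vaccine with no effect, which is the purpose the SAP gives for the looks.

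Four stronger readings might be inferred, and the documents do not support them.

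- *Partial follow-up makes Table 2 understate wrongful stopping.* The printed 0.149 already exceeds the 10–12% obtained under planned accrual, and the direction can reverse.
- *The 7% to 9% figure is the error.* It agrees with the enumeration; the table does not.
- *Type I error is inflated.* The looks gave no chance of stopping for efficacy.
- *The decisions taken at the looks were wrong.* No interim data are given, so nothing can be said about them.

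**Conclusion.** The point holds as a reporting defect in Appendix 3. As printed, Table 2 overstates cumulative stopping by look 2 by 5.5 to 11.9 points in every row, both when the vaccine works and when it does not, and understates final success. The second-look columns of Tables 1 and 3 share the fault. This rests only on the SAP's own algorithm and inputs, with N = 70 taken from SAP 4; N = 64 does not change it.

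The follow-up gap is a real but secondary limitation. The BPP as computed treats viremia seen so far as final status for subjects already counted, so it is not strictly the probability described in SAP 7.8. With equal timing and 27 to 32 months of assumed accrual the shift is roughly 1 to 3 points on wrongful stopping and 1 to 4 on no-effect stopping. It is larger if no data after month 6 are used and can change sign if timing differs between arms. No final estimate or test is affected.

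**What to change.** - Leave the futility rule and the 0.20 cutoff on record as applied; do not recalibrate for looks already held.
- Rerun Appendix 3, state the N used, and correct the second-look and end-of-study columns of Tables 1 to 3, including the Table 3 row that sums to 1.020.
- Keep the 7% to 9% and above-10% figures, labelled as cumulative by look 2, and label the figure of about 61% as first look.
- Add scenarios in which partial follow-up enters the data generation only, with stated onset and accrual assumptions and with equal and unequal timing between arms. Leave the BPP formula as it was applied.
- In the CSR, report the follow-up available at each look, and say that the BPP was computed on viremia observed to date.

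The cost is one simulation rerun and short edits to Appendices 2 and 3 and the CSR.
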